5.2.1 Six Minute Walk Distance

Walking is the most basic form of exercise and is integral to daily activities. The 6MWT is a standardized, times submaximal test of unencouraged, self-determined distance walked which is reliable and valid⁵⁴. Standardized test methods and scripted and timed statements have been established in prior studies of PAH^{28,29-35}. The 6MWT will be administered according to the Thoracic Society guidelines^{36,54}. The 6MWT will be performed at Visit 1, Visit 2 Visit 3 and Visit 4. The subject will be instructed to wear comfortable clothing and shoes. The test will be performed at approximately the same time of day at each visit. In addition, Borg dyspnea Score, oxygen saturation, and heart rate will be recorded at the beginning and conclusion of each test.

5.2.2 The Borg Dypsnea Score

In order to assess exercise capacity, the Borg score for dyspnea and overall fatigue will be recorded before and after subjects complete the six-minute walk, performed at Visit 1, Visit 2 visits and Visit 4 visits. This score is a measure the physical activity intensity level based on the subject's perceived exertion. Subjects will rate at resting and peak exercise.

5.2.3 WHO Functional Class

The WHO functional classification for PAH has been modified from the well-known New York Heart Association functional classification. This functional classification is based on symptoms, with Class I being defined by no symptoms, Class II as having mild limitation in physical activity, Class III as having markedly limited physical activity and Class IV as being unable to perform any physical activity. The WHO functional class will be assessed at Visit 1, Visit 2 visits and Visit 4 visits.

5.2.4 Blood Biomarkers

5.2.4.1 Lipid Metabolism

Fasting plasma lipid metabolites will be evaluated via non-targeted metabolomics screen. Mass spectroscopy metabolites such as LDL, HDL, and triglycerides will be performed at Visit 1, Visit 2, Visit 3 and Visit 4.

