5.1 Assessments of Efficacy

Primary Endpoint: Difference in plasma carnitine concentration from Visit 1 to Visit 4.

Secondary Endpoints:

- Quantify the prevalence of carnitine supplement use
- Measure oral ingestion of carnitine in PAH patients.
- Difference in six-minute walk test from Visit 1 to Visit 2.
- Difference in functional class from Visit 1 to Visit 2.
- Difference in plasma BNP from Visit 1 to Visit 2
- Difference in plasma carnitine concentration from Visit 1 to Visit 2.
- Correlation of plasma carnitine concentration with TMAO concentration.
- Difference in plasma acylcarnitines from Visit 1 to Visit 2.
- Difference in lipid metabolites from Visit 1 to Visit 2.
- Change in plasma carnitine from Visit 2 to Visit 3.
- Difference in RV function from Visit 2 to Visit 4.
- Difference in plasma acylcarnitine profile from Visit 2 to Visit 4.
- Difference in lipid metabolites from Visit 2 to Visit 4.
- Correlation of change in plasma carnitine with change in Functional class.
- Correlation of change in plasma carnitine with change in six minute walk distance.
- Correlation of change in plasma carnitine with change in BNP.
- Correlation of change in plasma carnitine concentration with TMAO concentration
- Correlation of change in plasma carnitine with change in markers of RV function including TAPSE and RV fractional area change.
- Markers of tolerability including presence of side effects, adverse events and serious adverse events.

- Pill counts at Visit 4 for adherence
- 5.2 Secondary Outcome Measures

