6.2 Statistical Analysis

The primary endpoint and other continuous endpoints will be summarized using the mean, standard deviation, the median, and interquartile range. We will use either the paired t-test or the Wilcoxon-signed rank test to assess the change from Visit 1 on these endpoints. Estimate of mean change along with its 95% confidence interval will be reported to quantify the treatment effect. To assess tolerability of carnitine, we will closely monitor any adverse events. For these binary events, proportion of subjects who experience the event will be calculated along with its 95% confidence interval. We will use the open-source statistical package R⁵⁷ for analyses.

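### The untargeted lipid screen is a secondary endpoint with no stated unit of analysis, no false-discovery control and no exploratory label

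*Combined protocol and SAP*

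**What the plan says.** Section 5.2.4.1 (Lipid Metabolism) describes the assay: "Fasting plasma lipid metabolites will be evaluated via non-targeted metabolomics screen". It then gives examples and timing: "Mass spectroscopy metabolites such as LDL, HDL, and triglycerides will be performed at Visit 1, Visit 2, Visit 3 and Visit 4". The number of metabolites is not stated.

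Section 5.1 lists two secondary endpoints from this assay: "Difference in lipid metabolites from Visit 1 to Visit 2" and "Difference in lipid metabolites from Visit 2 to Visit 4". In the Protocol Summary the supplement-period interval for the same endpoint is Visit 3 to Visit 4.

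Section 6.2 is the only analysis text that reaches these endpoints, and the Protocol Summary repeats it. Its scope is general: "The primary endpoint and other continuous endpoints will be summarized using the mean, standard deviation, the median, and interquartile range". The test is general too: "We will use either the paired t-test or the Wilcoxon-signed rank test to assess the change from Visit 1 on these endpoints". So is the estimate: "Estimate of mean change along with its 95% confidence interval will be reported to quantify the treatment effect".

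No section mentions false-discovery control, family-wise control, a testing hierarchy or an exploratory status for the screen. A 5% two-sided level appears only in the sample-size text for plasma carnitine (Section 6.1 and the Protocol Summary).

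**The concern.** Leaving about 20 named secondary endpoints unadjusted is a fair choice in a pilot of 10 patients. A reader can count them and discount a stray small p-value. A non-targeted screen is different. One line in the endpoint list stands for an open-ended number of comparisons, and the reader cannot discount for a number that is not given.

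If the generic rule is applied as it stands, the report could contain a list of lipids called changed, with no indication of how many would be expected by chance. Two further freedoms add to this. The contrast is not settled (from Visit 1, Visit 2 to 4, or Visit 3 to 4). The choice between t-test and Wilcoxon is also open, and at this sample size it largely decides whether any later error control can work.

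**Working it through.** **Inputs from the documents (Section 6.1).** n = 10; SD of plasma carnitine 11.1; within-subject correlation 0.7; SD of differences 8.6; change 8.5; two-sided 5%; power 80%.

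**Assumptions, because the documents are silent.** Number of metabolites m; share p that truly change; standardised effect d (mean change divided by the SD of the within-subject differences). Ranges are shown.

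**1. The plan's own figure.** SD of differences = 11.1 × √(2 × (1 − 0.7)) = 8.598, which rounds to 8.6. Exact paired t-test power (noncentral t, 9 df) is 79.4% at 8.5/8.6 and 80.3% at d = 1. The stated 80% is reproduced. It concerns plasma carnitine; no figure is given for the screen.

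**2. Chance findings per contrast if nothing changes.** Expected number = 0.05 × m.

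| m (assumed) | Expected false positives |
|---|---|
| 200 | 10 |
| 500 | 25 |
| 1,000 | 50 |

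A second contrast doubles these. Correlation among lipids alters the spread of the count, not its expectation.

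**3. False share among flagged metabolites.** Share = 0.05(1 − p) / [0.05(1 − p) + p × power]. Power at 5% is 0.803 for d = 1 and 0.293 for d = 0.5. Example, p = 5% and d = 1: 0.0475 / (0.0475 + 0.0402) = 54%.

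| p truly changed | d = 1 | d = 0.5 |
|---|---|---|
| 1% | 86% | 94% |
| 5% | 54% | 76% |
| 10% | 36% | 61% |
| 20% | 20% | 41% |

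The share is one half when p = 0.05 / (0.05 + power): 0.05 / 0.853 = 5.9% at d = 1, and 0.05 / 0.343 = 14.6% at d = 0.5.

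**4. The Wilcoxon floor.** With 10 pairs the smallest exact two-sided p is 2/1024 = 0.00195. Benjamini-Hochberg at 5% with m = 500 declares k metabolites if the k-th smallest p is at most 0.05k/500 = 0.0001k. Then k ≥ 0.00195 / 0.0001 = 19.5, so at least 20 must be declared together or none is. They need not all sit at the floor: the next attainable value is 4/1024 = 0.0039, and 40 metabolites at or below it also qualify, because 40 × 0.0001 = 0.0040. With m = 100 the minimum is 4 (0.00195 / 0.0005 = 3.9). The paired t-test has no such floor.

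**5. Effect of the proposed control.** Simulation of paired t-tests with Benjamini-Hochberg at 5% (1,000 runs, independent normal differences, n = 10, m = 500, p = 10%):

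| d | False share, unadjusted | False share, BH | Power per true metabolite, unadjusted | Power, BH |
|---|---|---|---|---|
| 1.0 | about 35% | about 4.5% | 80% | about 15% |
| 1.5 | about 31% | about 4.4% | 99% | about 78% |

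**The case against.** Several objections have force.

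- **The reading is inferred.** No section says that each metabolite is tested separately or at 5%. Section 6.2 stresses estimates with intervals and gives no rule for declaring a metabolite changed. This stands as a limit on the claim. Per-metabolite testing at 5% is still the natural reading of a test plus a 95% interval for every continuous endpoint.
- **Most findings would be false.** A reader might infer this, but the documents do not support it. It requires fewer than about 6% of metabolites truly changed at d = 1, or about 15% at d = 0.5, and neither the true share nor the effect size is given.
- **Wilcoxon rules out adjustment.** A reader might also infer this. It does not: the smallest p only sets a minimum number declared together, and Section 6.2 allows the t-test as well.
- **The lipid list will steer the next study.** The introduction ties the preparation for a mechanistic study to carnitine intake, stability and response to supplementation. Lipid markers are one of several physiologic readouts, and no decision hangs on the list.
- **Control is expensive at n = 10.** At d = 1, power per true metabolite falls from about 80% to about 15%. In a proof-of-concept study, which error to tolerate is partly a preference. This argues against discarding everything above a cut-off, but not against reporting q-values.

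**Conclusion.** The gap is real and narrow. An open-ended screen is a secondary endpoint at two contrasts, governed only by a generic test with unadjusted intervals, and nothing marks it as exploratory or limits false discoveries. If each metabolite is tested at 5%, about 5% of unchanged metabolites would be flagged by chance per contrast. The false share among those flagged could be large (86%, 54% or 36% at d = 1 when 1%, 5% or 10% truly change), but its size cannot be fixed from the documents. The counts rest on assumed numbers of metabolites, and the simulated power and error rates also assume independent metabolites with normal differences. The primary endpoint and its power are not touched. This is a minor change worth making because it costs little.

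**What to change.** In Section 6.2, and in the matching text of the Protocol Summary:

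1. State that the screen is analysed per metabolite at one named contrast, and reconcile the Protocol Summary (Visit 3 to 4), Section 5.1 (Visit 2 to 4) and Section 6.2 (from Visit 1).
2. Name one test: the paired t-test on log intensities. The log scale makes the estimate a ratio and should reduce skewness, which matters when small p-values rest on 10 pairs.
3. Report the number of metabolites tested, and the Benjamini-Hochberg q-value beside every estimate and confidence interval, not only for those below a cut-off.
4. Label the screen exploratory.
5. Pre-list a short set of acylcarnitines outside the screen. No endpoint names any at present, so the sponsor must choose them. Section 5.2.4.2 gives acylcarnitine profiles at Visits 1 and 2 only, while the schedule in Section 4.3 has them at all four visits; these need to agree with the chosen contrast.

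This takes a few lines of R and no new data. The price is fewer metabolites declared and lower power for each true one: about 80% to 15% at d = 1, or 99% to 78% at d = 1.5, with an assumed 500 metabolites and 10% changed. Showing all estimates with their q-values, under an exploratory label, keeps the weaker signals visible.

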5.2.4.2 Fatty Acid Metabolism

Elevated circulating fatty acids and acylcarnitines contribute to RV lipotoxicity. To evaluate the effect of this intervention on fatty acid metabolism, we will measure fasting long-chain fatty acid and acylcarnitine profiles using mass spectrometry at Visit 1 and Visit 2.

5.2.4.3 Plasma NT-proBNP

Plasma NT-proBNP reflects right ventricular function in PAH and is a strong predictor of outcome in PAH. BNP will be assessed at Visit 1, Visit 2, Visit 3, and Visit 4.

5.2.4.4 TMAO

Trimethylamine-N-oxide (TMAO) is associated with increased cardiovascular risk²⁷ and presents as a detrimental carnitine effect. As a safety endpoint, TMAO will be measured via mass spectroscopy.

5.2.5 Transthoracic Echocardiographic Measures

We will assess RV free wall longitudinal strain and other parameters as secondary endpoints via transthoracic echocardiography. The ultimate determinant of outcome in subjects with PAH is right ventricular function, so we have focused on metrics, which are predictors of survival in PAH, including RV strain and qualitative RV function. The following metrics will be obtained: 1) tricuspid annular plane systolic excursion (TAPSE); 2) RV & LV ejection fraction⁵¹; 3) RV fractional area change; 4) tricuspid annular velocity (S'); 5) tricuspid regurgitant (TR) velocity; 6) RV systolic pressure (estimated from the equation: RV systolic pressure = 4(maximum TR velocity)⁶¹ + right atrial pressure); 7) right atrial pressure⁵⁹; 8) RV & LV diastolic function⁵³; 9) RV free wall longitudinal strain^{54,60}. All measurements will be performed according to the American Society of Echocardiography guidelines^{51,53,59}.

5.2.6 Other Feasibility Endpoints

- a) Drop Out Rates
- b) Side effects and tolerability of supplementation including carnitine

5.2.7 Hospitalization

A hospital admission due to PAH progression and/or right-sided heart failure will be defined as a hospitalization because of lower extremity edema or dyspnea and/or PAH symptoms (e.g., syncope) refractory to outpatient increases in dose or frequency of diuretics or specific PAH medications.

We will record all hospitalizations during the time of the study. Records from each hospitalization will be obtained by the local study coordinator. These records will be reviewed by the Data and Safety Monitoring Board (DSMB), which is unrelated to the study.

5.2.8 Death

Cardiovascular Death: We define as cardiovascular death:

- 1) sudden death
- 2) death preceded by either one of the following:
 - a) cardiogenic shock defined by either:
 - i. hypotension resulting in a failure to maintain normal renal
 - ii. cerebral function for >15 minutes prior to death)
 - b) heart failure symptoms or signs requiring one of the following:
 - i. intravenous therapy or oxygen in the hospital

ii. confinement to bed in the absence of secondary causes (such as systemic infection or dysfunction of intravenous or subcutaneous medication delivery devices) or alternative causes of death.

Non-Cardiovascular Death: A death which does not meet the criteria above will be considered a non-cardiovascular death.

6 Statistical Considerations

6.1 Study Design

In a study for 28 PAH patients⁶ the mean \pm SD of plasma carnitine data was 38.6 \pm 11.1 uM. The data appeared to be normally distributed. In a pilot study²¹, L-carnitine supplementation increased free plasma carnitine concentration by 22% (Table 3 in²¹). A sample size of 10 will have 80% power to detect a within subject change in means of 8.5 (increase from Visit 1 mean of 38.6 to 47.1 after 2 weeks of treatment, representing a 22% increase) using a paired t-test with a 5% two-sided significance level. The standard deviation of within-subject differences is assumed to be 8.6 and it is calculated using SD of 11.1 assuming a moderate within-subject correlation 0.7. We plan to study 10 PAH patients in this proof-of-concept study. The study has 80% power to detect a within-subject change of effect size 1, i.e. change measured as 1 times of the SD.

6.2 Statistical Analysis

The primary endpoint and other continuous endpoints will be summarized using the mean, standard deviation, the median, and interquartile range. We will use either the paired t-test or the Wilcoxon-signed rank test to assess the change from Visit 1 on these endpoints. Estimate of mean change along with its 95% confidence interval will be reported to quantify the treatment effect. To assess tolerability of carnitine, we will closely monitor any adverse events. For these binary events, proportion of subjects who experience the event will be calculated along with its 95% confidence interval. We will use the open-source statistical package R⁵⁷ for analyses.

6.3 Subjects' retention and supplement compliance

We will enforce subject retention in several ways. We will record extensive contact information for each subject at their enrollment in the trial. This will include home, work, and cellular telephone numbers. The research coordinator will call before each study visit to remind the subject to attend. Subjects will be reimbursed for time at the clinic for research procedures and reasonable travel expenses necessary for their participation in the study. Subjects will receive \$75 each for Visit 1 and Visit 2, \$100 for Visit 3, and \$150 for Visit 4. The total reimbursement for completing all study procedures will be \$400.

The research coordinator and physician will explain the importance of compliance with the study protocol at each subject contact. If a subject fails to comply with a study visit, the coordinator will contact him or her by telephone. If this fails, the coordinator will send two letters, one week apart, to request follow-up.

We have considered how to minimize difficulties with adherence to the supplement. We will strongly emphasize the importance of complying with the supplement regimen. Nonetheless, we will perform pill counts at visits and record episodes when the supplement is withheld for any reason. If a subject wishes to drop-out from the supplement phase of the study or has a serious adverse event (SAE) (whether related to study drugs or not), we will continue to follow-up with the subject for study assessments to assist with safety monitoring and to avoid the problems introduced by missing data. The inclusion of such follow-up data will allow for analysis by intention-to-treat.

If a subject is withdrawn from the supplement portion of the study for any reason, the subject will be strongly encouraged to continue with the remainder of the study assessments, as scheduled.

6.4 Interim Monitoring Guidelines

We have not planned formal interim analyses for efficacy and therefore there are no stopping rules for efficacy for this trial. This project will have an independent safety officer who may consider whether to stop the trial or not if there is an increased risk of adverse events or toxicity.

6.5 Protocol Violations

Serious protocol violations such as discontinuation of the intervention unrelated to AEs will be carefully recorded and regularly reviewed by the Principal Investigator. Remedial changes in procedure will be recommended where feasible to reduce the incidence of such violations. When known, the causes and circumstances of all violations will be documented for future secondary analyses and interpretation. Because all primary analyses will be intent-to-treat, it is essential that violations be kept to a minimum especially where it is possible to influence their rate of occurrence.

6.6 Safety and masking analysis

All subjects will be assessed for toxicity and included in the safety analysis. This analysis will include summaries of the incidence and grade of toxicities. Safety interim analyses will be performed and reported to the DSMB. Subjects will be evaluated for SAEs.

7 Study Risks and Discomforts

7.1 Echocardiography

There are no risks to this ultrasound procedure aside from minor discomfort related to placement of the ultrasound probe on the chest.

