2.1 Objectives

This is a single-center, prospective study enrolling 10 PAH patients. All eligible participants will be given carnitine supplements for 2 weeks.

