4.2 Study Visits and Contacts

This study will consist of four visits: Visit 1 (0 week), Visit 2 (Week 12), Visit 3 (Week 12+1 day) and Visit 4 (Week 14). The Visit 1 and Visit 3 are both estimated to take approximately 2 hours each. Visit 2 and Visit 4 are both estimated to take approximately 4 hours each. Patients will be consented by the PI, a clinical research coordinator, or a research nurse. Patient's written consent and study procedures will take place at the Pulmonary Vascular Disease Clinic (CPVD), the Clinical Research Center (CRC), there will be no changes to a patient's medication regimen.

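### The carnitine adverse-event rate is not restricted to subjects who took carnitine, so anyone who leaves during the 12-week undosed lead-in distorts it, in either direction

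*Combined protocol and SAP*

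**What the plan says.** Section 2.1 sets the size and design: "This is a single-center, prospective study enrolling 10 PAH patients". Sections 4.2 and 4.3 place Visit 1 at week 0, Visit 2 at week 12, Visit 3 one day later and Visit 4 at week 14. Section 3.3 has carnitine handed out at Visit 2, and section 4.2.4 lists dosing at that visit. Section 4.2.5 also lists a two-week supply at Visit 3. On any of these readings, no subject has carnitine during the first 12 weeks.

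On safety, section 6.6 says "All subjects will be assessed for toxicity and included in the safety analysis" and adds "This analysis will include summaries of the incidence and grade of toxicities". Section 6.2 gives the purpose, "To assess tolerability of carnitine, we will closely monitor any adverse events", and the estimator, "For these binary events, proportion of subjects who experience the event will be calculated along with its 95% confidence interval". It does not name the interval method.

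No section defines a safety population by exposure. The population language elsewhere (sections 6.3, 6.5 and 9.2.4) is intention-to-treat. Section 5.2.6 lists "Drop Out Rates" as a feasibility endpoint, but no expected rate is given anywhere.

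The sections disagree on when adverse-event collection begins. Section 9.2.3.1 starts the reporting period at the first study procedure, and section 8.2 has subjects asked about events at every contact. The adverse-event row of Table 1 (section 4.3) is marked only from Visit 2 onward.

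**The concern.** A tolerability rate for carnitine should describe people who took it. Here the undosed lead-in is six times as long as the supplement period (12 weeks against 2), and a subject can join, complete Visit 1 and leave without taking a caplet. Section 9.2.4 allows withdrawal at any time. In addition, pregnancy is an exclusion, yet the only scheduled pregnancy test is at Visit 2, so an ineligibility could surface just before dosing.

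Such a subject cannot react to carnitine, but sections 6.2 and 6.6 taken together keep them in the proportion. With 10 patients, each one is a tenth of the denominator. Tolerability is a listed secondary endpoint, and the opening text presents the trial as preparation for a later mechanistic study, so the rate should mean what its label says.

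**Working it through.** **The plan's own figure.** The documents state no safety denominator, expected event rate or safety precision, so there is nothing to reproduce on this point. The one design calculation (80% power for the primary paired t-test with N = 10, change 8.5 and SD of differences 8.6) comes out at 79.4%. It plays no part here.

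**Inputs.** N = 10 (section 2.1); the proportion of subjects with an event and a 95% interval (section 6.2). Three quantities are assumed, because the documents give none of them:
- k = subjects who leave before any dose, taken as 0 to 3
- x = dosed subjects with an event after dosing
- m = undosed leavers with a recorded lead-in event

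Intervals are exact (Clopper-Pearson).

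**Formulas.** Read as written, the reported rate is (x + m)/10. The rate among exposed subjects is x/(10 − k).

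**Case 1: undosed leavers have no event (m = 0).** The reported rate is (10 − k)/10 of the exposed rate, that is 90%, 80% or 70% of it for k = 1, 2 or 3. For zero events the upper limit is 1 − 0.025^(1/n).

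| Set | n | Upper limit, 0 events | Rate and 95% CI, 2 events |
|---|---|---|---|
| All subjects (same as dosed only if k = 0) | 10 | 30.8% | 20.0% (2.5–55.6) |
| Dosed only, k = 1 | 9 | 33.6% | 22.2% (2.8–60.0) |
| Dosed only, k = 2 | 8 | 36.9% | 25.0% (3.2–65.1) |
| Dosed only, k = 3 | 7 | 41.0% | 28.6% (3.7–71.0) |

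**Case 2: undosed leavers have a lead-in event (m > 0).** Under sections 8.2 and 9.2.3.1 these events are collected, and section 9.2.1.2 counts intercurrent illness as an adverse event. The reported rate exceeds the exposed rate when m > xk/(10 − k). With x = 2 and k = 2 the threshold is 4/8 = 0.5, so a single such leaver reverses the direction:
- exposed rate: 2/8 = 25.0% (3.2–65.1)
- reported, m = 1: 3/10 = 30.0% (6.7–65.2)
- reported, m = 2: 4/10 = 40.0% (12.2–73.8)

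**Case 3: changing the denominator alone.** Suppose 8 subjects are dosed, 2 have an event after dosing and one other has only a lead-in event. With a dosed-only denominator but all events counted, the rate is 3/8 = 37.5% (8.5–75.5), against 2/8 = 25.0% for events after dosing. The numerator therefore needs a rule as well.

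**The case against.** The best defence is that section 6.6 concerns toxicity, which presupposes exposure. Section 2.1 has every eligible participant receive the supplement, and the adverse-event row of Table 1 starts at the dosing visit. On that reading, *all subjects* means those who reach the supplement period. This is a possible intention, but the text does not state it. Sections 8.2 and 9.2.3.1 point the other way on timing, and the intention-to-treat language favours keeping everyone.

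It is also fair that the effect is small at this sample size and vanishes if nobody leaves undosed. Relatedness and pill counts are recorded, so an exposed-only rate could be rebuilt from 10 records. That stands as a limit on the harm. It does not settle which rate is the planned one, and leaves that choice open after the data are seen.

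Three stronger readings are tempting, and the documents do not support them:
- **That the error always flatters carnitine.** Case 2 shows that it can go the other way, because lead-in events are collected.
- **That the plan classes undosed subjects as having tolerated carnitine.** It says no such thing. This is only the arithmetic effect for undosed subjects with no recorded event.
- **That the plan expects loss before dosing because drop-out is an endpoint.** Measuring drop-out is not predicting it. The follow-up provisions in sections 6.3 and 9.2.4 concern withdrawal from the supplement phase.

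Nor do the documents say that the adverse-event rate will be used to design the later study.

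**Conclusion.** The point holds as a defect in a stated rule. As written, sections 6.2 and 6.6 give a proportion that is not a carnitine tolerability rate whenever someone leaves undosed, and no other section supplies an exposed set. For 1 to 3 undosed, event-free leavers out of 10, the zero-event upper limit is understated by 2.8, 6.1 or 10.2 percentage points (33.6, 36.9 or 41.0 minus 30.8). Lead-in events among leavers can push the rate up instead, for example to 40.0% against 25.0%.

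These sizes rest on assumed values of k, x and m and on exact intervals. With k = 0 the denominators agree, although lead-in events in dosed subjects would still need to be kept out of the numerator. The shift is modest beside intervals that span more than 50 percentage points when two events occur. It is worth correcting because the remedy is simple; it does not threaten the trial.

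**What to change.** In sections 6.2 and 6.6:
- Define the carnitine safety set as subjects who took at least one dose, and use it as the denominator for every tolerability and toxicity proportion.
- Count in the numerator only adverse events that start or worsen after the first dose.
- List lead-in adverse events and undosed withdrawals separately, so that nothing collected is lost.
- Name the confidence interval method; an exact one suits N = 10.

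Reconcile the start of adverse-event collection in Table 1 (section 4.3) with sections 8.2 and 9.2.3.1. Reconcile sections 3.3 and 4.2.5 on when the supply is handed out, so that the first-dose date is recorded the same way for everyone.

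The cost is a few sentences of text, plus a slightly wider interval if anyone leaves before Visit 2.
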